## 2.5. Scientific and clinical justification of the protocol

Without treatment, DBA progresses to critical anemia in over four-fifths of all cases. Even with treatment, approximately half of patients will either fail to respond, do not have a durable response, or are unable to continue therapy due to steroid-associated toxicities. For these patients, chronic transfusions with the risk of cardiovascular, hepatic, endocrinologic, and other systemic organ dysfunction and a major impact on quality of life is the only management option with proven benefit. Yet, even with chelation therapy, due to long-term toxicities of chelators and iron loading, coupled with the effects of chronic anemia upon growth and development, cardiovascular health, and neurodevelopment, leads to a reduced life expectancy in DBA. HSCT remains the only definitive treatment for the hematologic complications of DBA. Yet, despite significant advances in

preparative regimens, supportive care, and management of complications, HSCT continues to carry significant morbidity and mortality, especially in the heavily pre-transfused population. In addition, many patients do not have available and sufficiently-matched related or unrelated donors. As a result of these complications of the disease and a paucity of effective alternative treatments, novel treatments for patients with DBA are acutely needed.

As discussed above (§2.1), DBA represents a spectrum of diseases caused by a variety of mutations in at least 21 genes affecting multiple different cellular pathways, but all converging on an excess of iron-containing heme pigment within the erythroid progenitors leading to iron accumulation and subsequently toxic levels of reactive oxygen species. With time, the accumulation of toxic intracellular and extracellular species causes a general bone marrow failure, leading to progressive cytopenias and bone marrow failure. Additionally, the chronic transfusions used to treat the most-affected of these patients further increases the marrow iron loading, exacerbating the cellular damage in addition to the non-hematologic complications of therapy.

Eltrombopag, in addition to stimulating the proliferation and differentiation of hematopoietic lineages, is a potent chelator of intracellular and extracellular iron, with activity demonstrated both *in vitro* and *in vivo* (§2.4.2). We hypothesize that this iron-depleting activity reduces the intracellular iron burden and thus the oxidative stresses upon the progenitor cells, thus leading to the clinical response we have seen in our single previously-treated DBA patient (§2.4.1). Therefore, based upon safety evidence provided by prior clinical trials and efficacy suggested by pre-clinical data and our clinical experience, we propose this study to demonstrate that by targeting the common pathway of DBA, this effect should be generalizable to all DBA patients and thus provide a novel treatment paradigm for DBA that will reduce or eliminate the transfusion burden and steroid side effects that plague DBA patients.

DBA, as noted above, is a cancer-predisposition syndrome (§2.2) including both solid tumors and hematologic malignancies. Although the biology of this predisposition is poorly understood, it likely represents genotoxic stress from the same toxic processes that lead to erythroid aplasia. In the marrow, the combined hematopoietic stresses of ineffective hematopoiesis, ongoing cellular damage leading to cytopenias and likely driving clonal progression, oxidative stress of free heme, and increased total body iron burden, especially within the marrow compartment, predisposes to dysplasia and malignant transformation. Although beyond the immediate scope of this trial, we hypothesize that by reducing these combined stresses, EPAG treatment will reduce the risk of hematopoietic and even non-hematologic malignancies in DBA. Furthermore, by reducing the need for HSCT, EPAG may have the secondary effect of reducing the risk of treatment-related morbidity, malignancies, and mortality.

The primary objective of this trial will be to evaluate the safety and efficacy of eltrombopag as a single agent in subjects with Diamond-Blackfan anemia, especially patients with relapsed disease,

refractory disease, or patients who cannot tolerate ongoing standard therapies. The secondary objectives of this trial will include assessments of the impact of eltrombopag upon rates of relapse and survival, clonal evolution, toxicities of extended therapy, the impact of treatment upon health-related quality of life and neurodevelopment in pediatric patients, and the impact of eltrombopag upon stem cell and erythroid cell dynamics and niche interactions including iron homeostasis.

# 3. Study Design

The study is designed as a single-site, non-randomized, single-arm pilot study of the oral TPOR agonist eltrombopag (EPAG) in Diamond-Blackfan anemia (Figure 3) to test the hypothesis: *eltrombopag improves the production of red blood cells in Diamond-Blackfan anemia patients.* The primary endpoint (see §8.2) is measured at 6 months (24 weeks ± 14 days). Subjects who cannot tolerate the medication or fail to respond by the primary endpoint will be taken off study drug. Subjects who *respond* at the primary endpoint (hemoglobin increase of 1.5 g/dL or more and/or transfusion independence for the previous 8 weeks, see §8.2.1) will be able to continue EPAG on the extension part of this protocol for an additional 3 years. During the 3-year extension phase, subjects will remain on the same dose of EPAG until they reach a *robust response* (defined as hemoglobin ≥10 g/dL in the absence of transfusions for more than 8 weeks, see §8.2.1). Drug dose will then be tapered slowly to the lowest dosage that maintains a stable hemoglobin (≥ 10 g/dL) and eventually discontinued if possible (per §5.3), until they meet off study criteria (see §8.6), or the study is closed. Drug will be restarted during extension if robust response is lost (*i.e.* hemoglobin falls below 9 g/dL).

Up to 30 subjects (18 for Stage 1 & 12 for Stage 2) will be screened to accrue 25 eligible subjects for this study.

[figure not shown]

Figure 3: Study enrollment and treatment schema

#### 4. Eligibility Assessment

#### 4.1. Inclusion criteria

In order to be participate in this study, individuals must meet all of the following criteria:

- 4.1.1. Diamond-Blackfan anemia defined as anemia presenting on or before the third year of life with reticulocytopenia and greatly reduced or absent bone marrow erythroid precursors, supported by, but not requiring either:
  - familial history
  - gene mutation testing demonstrating a known disease-causing mutation or a mutation of disease-associated gene in combination with clinical characteristics of DBA

Patients with late-onset DBA (diagnosed after the third year of life) may also be included if gene mutation testing confirms a disease-causing mutation as above.

- 4.1.2. Clinically-significant anemia as defined as either:
  - hemoglobin less than 9.0 g/dL
  - red cell transfusion of at least 2 units PRBC for adults or 30 cc/kg for children (whichever is less) in the eight weeks prior to study enrollment
- 4.1.3. Relapsed and/or steroid-refractory or intolerant of systemic corticosteroids
- 4.1.4. Age  $\geq$  2 years
- 4.1.5. Weight  $\geq$  12 kilograms
- 4.1.6. Residence within the United States of America or territories, or able to reside within the US or its territories while on drug during trial participation

## 4.2. Exclusion criteria

Individuals meeting any of the following criteria will not be eligible for participation in this study. However, having met exclusion criteria in the past does not preclude study participation if the criteria are no longer met, unless otherwise specified (*i.e.* patients with modifiable factors such as laboratory abnormalities or acute health problems may be re-screened). For laboratory assessments, this requires no less than two weeks from the previous exclusionary finding. The intervals for health problems that must elapse prior to re-screening are specified below.

4.2.1. Platelet count > 400,000 /  $\mu$ L

- 4.2.2. Stage 4 or greater kidney disease as defined by creatinine > 2.5 mg/ dL or GFR < 30 mL/min/1.73 m^2
  - 4.2.2.1. For pediatric patients 17-years-old or younger, GFR shall be used. This can be estimated using the bedside Schwartz equation, the Counahan-Barratt method, or a similar methodology. Direct measurement including, but not limited to, 24-hour urine creatinine clearance or radiographic methods is recommended for patients with stage 3 disease (GFR  $\leq$  45 mL/min/1.73 m^2).
- 4.2.3. Direct bilirubin > 2.0 mg/ dL, including congenital abnormalities in the bilirubin level
- 4.2.4. SGOT (AST) or SGPT (ALT) > 5 times the upper limit of normal
- 4.2.5. Treatment with androgens (danazol or oxymetholone) or corticosteroids less than 4 weeks prior to initiating eltrombopag.
  - 4.2.5.1. Physiologic steroid replacement for adrenal insufficiency or other similar conditions is not exclusive of trial participation
- 4.2.6. Treatment with any medications that may interfere with the metabolism of eltrombopag (e.g., CYP1A2 and CYP2C8 modulators) or whose own altered metabolism by eltrombopag cannot be adjusted for (see §5.8, 5.9, and 10.3.1)
- 4.2.7. Hypersensitivity to eltrombopag or its components
- 4.2.8. Moribund status or concurrent hepatic, renal, cardiac, neurologic, pulmonary, infectious, or metabolic disease of such severity that it would preclude the patient's ability to tolerate protocol therapy, or that death within 7-10 days is likely
- 4.2.9. Life expectancy of less than 3 months for any cause
- 4.2.10. Subjects with known liver cirrhosis in severity that would preclude tolerability of eltrombopag as evidenced by albumin < 3.5g/dL
- 4.2.11. History or current diagnosis of cardiac disease indicating significant risk of safety for patients participating in the study such as uncontrolled or significant cardiac disease, including any of the following:
  - Recent myocardial infarction (within last 6 months),
  - Uncontrolled congestive heart failure,

- Unstable angina (within last 6 months),
- Clinically significant (symptomatic) cardiac arrhythmias (e.g., sustained ventricular tachycardia, and clinically significant second or third-degree AV block without a pacemaker.)
- Long QT syndrome, family history of idiopathic sudden death, congenital long QT syndrome or additional risk factors for cardiac repolarization abnormality, as determined by the investigator
- Impaired cardiac function such as corrected QTc>450msec using Fridericia correction on the screening EKG, other clinically significant cardio-vascular disease (e.g. uncontrolled hypertension, history of labile hypertension), history of known structural abnormalities (e.g. cardiomyopathy).
- 4.2.12. Known active or uncontrolled infections not adequately responding to appropriate therapy.
  - 4.2.12.1. HIV infection is not exclusive of trial participation if the infection is effectively controlled with medications not known to interfere with eltrombopag metabolism or be metabolized by pathways known to be altered by eltrombopag (as per §4.2.6). HIV RNA viral load must be undetectable at the time of enrollment, and CD4 cell count must be  $\geq 200/\mu$ L. Patients must remain on antiretroviral therapy throughout study participation and must be periodically monitored for suppression of viral load and CD4 cell count. If drug-drug interactions between antiretroviral medications and eltrombopag are suspected, these must be addressed by a qualified clinical pharmacist or pharmacologist, and any changes to antiretroviral therapy need to be approved in consultation with an Infectious Disease and/or HIV specialist prior to enrollment.
- 4.2.13. Active malignancy or likelihood of recurrence of malignancies within 12 months
- 4.2.14. Evidence for MDS or AML as defined by WHO criteria.
- 4.2.15. Patients who have received chemotherapeutic treatment or other specific antineoplastic drugs or radiation therapy within 6 months of study entry
- 4.2.16. Female subjects who are nursing or pregnant (positive serum or urine β-human chorionic gonadotrophin (b-hCG) pregnancy test) at screening or pre-dose on Day 1.
- 4.2.17. Women of child-bearing potential, defined as all women physiologically capable of becoming pregnant, unless they are using highly effective methods of

contraception during dosing and for 30 days after the last dose of eltrompobag. Highly effective contraception methods include:

- Total abstinence (when this is in line with the preferred and usual lifestyle of the patient. Periodic abstinence (e.g., calendar, ovulation, symptothermal, post-ovulation methods) and withdrawal are not acceptable methods of contraception
- Female sterilization (have had surgical bilateral oophorectomy with or without hysterectomy), total hysterectomy or tubal ligation at least six weeks before taking study treatment. In case of oophorectomy alone, only when the reproductive status of the woman has been confirmed by follow up hormone level assessment
- Male sterilization (at least 6 months prior to screening). For female patients on the study the vasectomized male partner should be the sole partner for that patient.
- Use of oral, injected or implanted hormonal methods of contraception or placement of an intrauterine device (IUD) or intrauterine system (IUS), or other forms of hormonal contraception that have comparable efficacy (failure rate <1%), for example hormone vaginal ring or transdermal hormone contraception.
- In case of use of oral contraception women should have been stable on the same pill for a minimum of 3 months before taking study treatment.
- Women are considered post-menopausal and not of child bearing potential if they have had over 12 months of natural (spontaneous) amenorrhea with an appropriate clinical profile age appropriate (e.g. generally 40-59 years), history of vasomotor symptoms (e.g. hot flushes) in the absence of other medical justification or have had surgical bilateral oophorectomy (with or without hysterectomy), total hysterectomy or tubal ligation at least six weeks ago. In the case of oophorectomy alone, only when the reproductive status of the woman has been confirmed by follow up hormone level assessment should she be considered not of childbearing potential.
  - Sexually active males unless they use a condom during intercourse while taking the study treatment and for 30 days after stopping study treatment and should not father a child in this period. A condom is required to be used also by vasectomized men as well as during intercourse with a male partner in order to prevent delivery of the drug via seminal fluid.
- 4.2.18. History of thromboembolic events other than catheter-related thromboses

Page 26 of 97

4.2.19. Active alcohol/drug abuse

- 4.2.20. Unable to understand the investigational nature of the study or give informed consent and does not have a legally authorized representative or surrogate that can provide informed consent
- 4.2.21. Unable to take investigational drug
- 4.2.22. Concurrent participation in an investigational study within 30 days prior to enrollment or within 5-half-lives of the investigational product, whichever is longer. Note: parallel enrollment in a disease registry is permitted.

#### 5. Treatment Plan

5.1. Administration of study drug (eltrombopag)

Subjects will initiate EPAG at a starting daily dose as detailed below, according to age and ethnicity. Subjects 12 years of age and above will receive the adult dose of 150 mg. Those between 6 and 11 will start at 75 mg, and children 2 and 5 years of age will start at 2.5 mg/kg, not to exceed 75 mg (Table 1).

To adjust for the higher expected exposure in subjects of East Asian and South East Asian ancestry, the starting dose for East Asian and South East Asian subjects 12 years of age and above will be 75 mg once daily. For East Asian and South East Asian subjects between 6 and 11 years of age, the starting dose will be 37.5 mg once daily, and for children between 2 and 5, the starting dose will be 1.25 mg/kg (Table 1).

Age group Daily dose		
	Non-Asian	
≥12	150 mg	
6-11	75 mg	
2-5	2.5 mg/kg, max 75 mg	
East Asian, South East Asian		
≥12	75 mg	
6-11	37.5 mg	
2-5	1.25 mg/kg, max 37.5 mg	

Table 1: Starting daily dose of eltrombopag according to age and ethnicity

Eltrombopag dose may be interrupted when clinically indicated at the discretion of the investigator. If EPAG dosing is delayed or interrupted for more than 1 week (7 days) and the interruption is not the result of a severe adverse event related to EPAG, then the subject will receive EPAG for additional time in order to receive a total of 24 weeks as originally planned. Interruptions shall be recorded in the medical record. Whether interruptions are reported (e.g. as deviations or adverse events) shall be determined as per Policy 801.

# Medication dosing errors, dose delays or dosing interruptions:

Interruptions such as delays in request for medication refills or medication errors by subjects, unless they result in a serious adverse event or impact the integrity of the research data, will not be considered as deviations, but will be recorded in the medical record.

# 5.2. Dose adjustments of eltrombopag

Platelet Count	Dose Adjustment or Response
≥400,000/µL (untransfused) at any time on study	Decrease dosage by 25 mg/day (or 12.5 mg in children under 12) every 2 weeks (± 3 days) to highest dosage that maintains hemoglobin ≥9 g/dL without increasing platelet count ≥400,000/µL. For subsequent elevations over 400,000/µL, the dose may be reduced by up to 50%.
≥600,000/µL (untransfused) at any time on study	Discontinue eltrombopag for one week (± 3 days); when platelets fall to <400,000/µL, restart at dosage decreased by at least 25 mg/day (or 12.5 mg in children under 12) or up to 50%.

# Table 2: Criteria for the adjustment of the daily dose of eltrombopag

## 5.3. Taper of eltrombopag in the extension protocol

Once a robust blood count recovery occurs in the extension part (*i.e.* hemoglobin >10 g/dL in the absence of transfusions for more than 8 weeks), EPAG dose will be tapered according to Table 3. If hemoglobin falls to <9 g/dL or the patient again requires RBC transfusions then EPAG will be either re-initiated or the dose will be increased to the last effective strength.

Age group	Starting dose	Step 1	Step 2	Step3	Step 4
		Non-Asia	an		
≥12	150 mg	75	37.5	25	stop
6-11	75 mg	37.5	25	12.5	stop
2-5	2.5 mg/kg	1.25mg/kg	stop		
East Asian, South East Asian					
≥12	75 mg	37.5	25	12.5	stop
6-11	37.5 mg	25	12.5	stop	
2-5	1.25 mg/kg	stop			

# Table 3: Eltrombopag taper in the extension protocol

Each step is 8 weeks

5.4. Dose delays, modifications or discontinuation for non-hematologic side effects

## 5.4.1. Infection

Subjects who experience an infection requiring intravenous antibiotics will not have EPAG discontinued. If the subject experiences infection severe enough to require vasopressors or intubation, the drug will be withheld until the patient is stable.

#### 5.4.2. Liver function abnormalities

Recommended dose modifications for isolated ALT or AST elevation are listed in Table 4.

Table 4: Eltrombopag dose modifications for isolated ALT or AST elevation

Elevation	Dose modification and Follow-up	
>ULN - 3.0 x ULN	Maintain dose level.	
>3.0 – 5.0 x ULN	Maintain dose level.	
	Repeat liver function tests as soon as possible, preferably within 48-72	
	hours, from awareness of the abnormal results. Monitor liver function	
	tests weekly or more frequently if clinically indicated until resolved to $\leq$	
	3.0 x ULN.	
>5.0 – 10.0 x ULN	Interrupt dose.	
	Repeat liver function tests as soon as possible; preferably within 48-72 hours	
	from awareness of the abnormal results. Monitor liver function tests	
	weekly, or more frequently if clinically indicated until resolved to $\leq$ 3.0 x	
	ULN then:	
	If resolved in ≤ 14 days , maintain dose level.	
	If resolved >14 days , restart eltrombopag at a dose level 25mg/day	
	(12.5mg/day for children under 12) lower than the prior dose.	
>10.0 – 20.0 x ULN	Interrupt dose.	
	Repeat liver function tests as soon as possible, preferably within 48-72 hours	
	from awareness of the abnormal results. Monitor liver function tests	
	weekly, or more frequently if clinically indicated until resolved to	
	baseline.	
	If resolved, restart eltrombopag at a dose level 25mg/day (12.5mg/day for children under 12) lower than the prior dose.	
>20.0 x ULN	Discontinue subject from study drug treatment.	
	Repeat liver function tests as soon as possible, preferably within 48-72	
	hours from awareness of the abnormal results. Monitor liver function	
	tests weekly or more frequently if clinically indicated until resolved to	
	baseline or stabilization over 4 weeks.	

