# 8.6. Off study criteria

*Per subject choice:* Subjects may withdraw from study at their request. The risks of withdrawing will be discussed, as will alternative treatment options. Those subjects who choose to withdraw while taking eltrombopag will be strongly encouraged to continue to have labs monitored until he/she initiates alternative therapy.

**Per principal investigator decision:** Should any of the following events occur during the study period, or in the extension treatment arm in responders, EPAG will be discontinued. The subject will be followed until resolution of the event. For study purposes labs relevant to the adverse event will be monitored for 30 days after discontinuation of EPAG. We will offer patients a follow-up evaluation at the NIH 6 months following being taken off EPAG treatment either due to lack of response or because they met other criteria for coming off study, but this visit will not be required. If they do not return to the NIH, we will contact their primary hematologist for information on their current hematologic status 6 months following their final dose of eltrombopag, and then take

them off study. If a patient initiates an alternative disease directed therapy at any time, the subject's participation on this study will be considered complete and the subject will go off study.

- Intolerance of EPAG not resolved by dose reduction
- Life threatening acute hypersensitivity reaction
- Thrombosis/embolism (DVT, PE, stroke or TIA, myocardial infarction) other than central line thrombosis
- Persistent hepatotoxicity as defined in §10.3.1
- New or worsening morphological abnormalities or cytopenia(s) indicative for transformation to MDS or AML
- No treatment response by week 24 (+/- 7 days)
- Any Grade IV toxicity considered related to the study medication excluding readily reversible metabolic or laboratory abnormalities or hematologic toxicities (see §9.2.1, 10.3.1)
- Significant progression of disease such as development of a solid tumor while on EPAG, or a concomitant condition that would make the subject ineligible for further protocol participation
- Pregnancy or unwillingness to use acceptable forms of contraception
- Initiation of non-protocol therapy for Diamond-Blackfan anemia
- Subject non-compliance
- Lost to follow-up

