# Hepatotoxicity

PROMACTA may increase the risk of severe and potentially life-threatening hepatotoxicity. Measure serum ALT, AST, and bilirubin prior to initiation of PROMACTA, every 2 weeks during the dose adjustment phase, and monthly following establishment of a stable dose. PROMACTA inhibits UDP-glucuronosyltransferase-1A1 (UGT1A1) and organic anion-transporting polypeptide-1B1 (OATP1B1), which may lead to indirect hyperbilirubinemia. If bilirubin is elevated, perform fractionation. Evaluate abnormal serum liver tests with repeat testing within 3 to 5 days. If the abnormalities are confirmed, monitor serum liver tests weekly until resolved or stabilized. Discontinue PROMACTA if ALT levels increase to greater than or equal to 3 x ULN in patients with normal liver function or greater than or equal to 3 x baseline (or greater than 5 x ULN, whichever is the lower) in patients with pre-treatment elevations in transaminases and are:

- progressively increasing, or
- persistent for greater than or equal to 4 weeks, or
- accompanied by increased direct bilirubin, or
- accompanied by clinical symptoms of liver injury or evidence for hepatic decompensation.

If the potential benefit for reinitiating treatment with PROMACTA is considered to outweigh the risk for hepatotoxicity, then consider cautiously reintroducing PROMACTA and measure serum liver tests weekly during the dose adjustment phase. Hepatotoxicity may reoccur if PROMACTA is reinitiated. If liver test abnormalities persist, worsen, or recur, then permanently discontinue PROMACTA.

Isolated cases of severe liver injury were identified in clinical trials. The elevation of liver laboratory values occurred approximately three months after initiation of PROMACTA. In all cases, the event resolved following PROMACTA discontinuation.

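### Table 4 holds the eltrombopag dose for ALT >3.0–5.0 x ULN with no time limit, while 8.6 requires a stop for persistent hepatotoxicity, most naturally read as four weeks at this level

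*Combined protocol and SAP*

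**What the plan says.** Three places in the combined protocol and SAP bear on a raised ALT.

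- **5.4.2, Table 4.** The table is introduced with "Recommended dose modifications for isolated ALT or AST elevation are listed in Table 4". For values above 3.0 and up to 5.0 x ULN the action is "Maintain dose level". Tests are repeated, preferably within 48–72 hours, and staff then monitor liver function "tests weekly or more frequently if clinically indicated until resolved to" 3.0 x ULN or lower. The row has no maximum duration, no action if the value stays up, and no pointer to 8.6 or 10.3.1. The next two rows interrupt dosing. Only the last, above 20 x ULN, ends treatment.
- **8.6.** "Should any of the following events occur during the study period, or in the extension treatment arm in responders, EPAG will be discontinued". One listed event is "Persistent hepatotoxicity as defined in §10.3.1".
- **10.3.1, Hepatotoxicity.** "Discontinue PROMACTA if ALT levels increase to greater than or equal to 3 x ULN in patients with normal liver function". With raised pre-treatment transaminases the threshold is "greater than or equal to 3 x baseline (or greater than 5 x ULN, whichever is the lower". One of four further conditions must also hold, and any one is enough. The second is "persistent for greater than or equal to 4 weeks, or".

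Section 10.3.1 also permits cautious reintroduction when benefit is judged to outweigh risk, and calls for a permanent stop if liver abnormalities then continue, get worse or come back.

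**The concern.** Staff who adjust doses will work from Table 4, which reads as a complete ladder from no change through interruption to permanent stop. Followed as printed, it keeps a subject on an unchanged dose for as long as ALT stays between 3 and 5 x ULN. Section 8.6, read with 10.3.1, takes the same subject off drug at four weeks.

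Other parts of the plan make the slip easier:

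- Section 5 repeats some 8.6 stops where dosing staff will see them: thrombosis in 5.5.1 and new blood-smear abnormalities in 5.5.2. Persistent hepatotoxicity is not repeated.
- For the extension, 5.6 sends stopping and restarting decisions to 5.2, 5.3 and 5.4 without naming 8.6. Section 3 does name 8.6, so the plan points both ways.

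At stake is continued full-dose exposure in a subject who should have stopped. Hepatotoxicity carries a boxed warning (10.3.1). Raised ALT was the most frequent adverse event leading to withdrawal in the long-term ITP study described in 2.4.6. This trial enrols from age 2.

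**Working it through.** The plan gives no figure to reproduce. The check sets the rules side by side and then asks at which baseline values they overlap.

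**Step 1. The two rules**

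| | Table 4, row >3.0–5.0 x ULN | 8.6 with 10.3.1 |
|---|---|---|
| Force | recommended | mandatory |
| Analyte | ALT or AST | ALT only |
| Trigger, normal baseline | >3.0 to 5.0 x ULN | ≥3 x ULN |
| Duration | no limit | ≥4 weeks |
| Action | keep dose, test weekly | discontinue |

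The restriction of Table 4 to isolated elevations does not reconcile the two. The four conditions in 10.3.1 are alternatives, so the four-week condition applies even with normal bilirubin and no symptoms. The conflict concerns ALT only, because the 10.3.1 thresholds are set on ALT.

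**Step 2. A worked case**

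Take a subject with normal baseline and isolated ALT of 4 x ULN, found on day 0 and still present on weekly tests at weeks 1, 2, 3 and 4.

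- Table 4 at week 4: 3.0 < 4 ≤ 5.0, so keep the dose.
- 10.3.1 at week 4: 4 ≥ 3 and duration 4 ≥ 4 weeks, so discontinue.

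**Step 3. Dependence on baseline**

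Let b be an elevated baseline ALT in multiples of ULN. The 10.3.1 threshold is T(b) = min(3b, 5). The conflict band inside the Table 4 row runs from T(b) to 5.0, with width 5 − T(b).

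| Baseline | T(b), x ULN | Conflict band | Width |
|---|---|---|---|
| normal | 3.0 | 3.0–5.0 | 2.0 |
| 1.2 | 3 × 1.2 = 3.6 | 3.6–5.0 | 1.4 |
| 1.5 | 3 × 1.5 = 4.5 | 4.5–5.0 | 0.5 |
| 1.6 | 3 × 1.6 = 4.8 | 4.8–5.0 | 0.2 |
| 5/3 ≈ 1.67 | 5.0 | closes | 0 |

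Above 1.67 x ULN the 10.3.1 threshold is more than 5 x ULN, where Table 4 already interrupts dosing. Exclusion 4.2.4 removes only patients above 5 x ULN, so subjects with baselines between about 1.67 and 5 x ULN can enter and are not affected.

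**Step 4. Whether another rule closes the gap**

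The automatic stop for laboratory values above grade 2 in 9.2.2 exempts ALT and AST, so it does not.

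**The case against.** The strongest reply is that the two rules can both be obeyed. Table 4 only recommends, and its row is silent on duration; it does not say to continue regardless. Section 8.6 is mandatory and expressly covers the extension. Staff can hold the dose, test weekly and stop when 8.6 is met, and the investigator reviews outside results (6.3). This stands as a matter of construction: if 8.6 is applied alongside the table, there is no excess exposure. What remains is that the row used for dosing does not mention the stop.

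A second reply also has force. Section 10.3.1 never defines persistent hepatotoxicity by that name, and its rule for abnormalities that continue after reintroduction is another possible referent. The four-week condition is the more natural reading, not the only one. That uncertainty is a further reason to write the criterion into the row.

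A reader might infer more than the text supports:

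- **That 8.6 also imports the 10.3.1 condition on steadily rising ALT.** It names persistence only, and no size or number of rises is defined.
- **That 8.6 and 10.3.1 should override all of Table 4.** This could remove the restart that the >5.0–10.0 x ULN row allows when resolution takes more than 14 days.
- **That the ITP extension study gives an expected count.** Its five ALT withdrawals among 302 patients were not limited to this band, and came over a median 2.4 years at a median 50.4 mg/day. Here the primary period is 24 weeks and the usual starting dose is 150 mg/day from age 12. The rate does not carry over.

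**Conclusion.** The inconsistency is real and should be corrected. It covers isolated ALT elevation across the full 3–5 x ULN band at normal baseline, narrows as baseline rises, and disappears above about 1.67 x ULN. The conclusion assumes that the four-week condition in 10.3.1 is what 8.6 refers to, and that some staff will dose from Table 4 alone.

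The share of subjects who would hold ALT in this band for four weeks is not in the documents, and no estimate is offered. Extra exposure is also left uncounted. A tally to week 24 might look like an upper bound but would not be one, since responders may continue for three more years. If 8.6 is applied alongside the table, the excess is zero.

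It would go too far to say that the protocol orders treatment to continue in the face of persistent hepatotoxicity. Its binding text says the opposite, and the weakness is that the dosing table does not carry it. No effect on power, type I error or the response rate is claimed.

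**What to change.** Add to the >3.0–5.0 x ULN row of Table 4: *If ALT remains ≥3 x ULN (normal baseline) or ≥3 x baseline (elevated baseline) for ≥4 weeks, discontinue EPAG per 8.6/10.3.1.*

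State in 5.4.2 or 8.6 whether the reintroduction described in 10.3.1 is allowed after that stop. Leave the other Table 4 rows as they are.

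The change is to wording, through an amendment that needs IRB approval before use. It adds no tests, because weekly testing is already required in this band and the four-week point will be observed. The small downside is that a few subjects with stable, mild ALT elevation would stop earlier than under the table alone.
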